1.5.9 Outcome Variables

The outcome measures are outlined in Table 3. The primary outcome is sudden death and death due to ventricular arrhythmia at 3 months (90 days) after randomization. We will use the following definition of Sudden Death:

For witnessed deaths, sudden cardiac death will be defined as an unexpected, non-traumatic, nonself-inflicted fatality in otherwise stable participants who die within one hour of the onset of the terminal symptoms. For persons dying more than one hour after a cardiac arrest from a ventricular arrhythmia, the Non-Sudden Death due to Ventricular Arrhythmia category should be used.

For unwitnessed deaths, participants will meet the definition of sudden death if they are found dead within 24 hours of being well, assuming there is no evidence of another cause of death during that time period. Device arrhythmia and autopsy results may be used when available. For unwitnessed deaths when the participant was found dead more than 24 hours after last being seen, no device arrhythmia data are available, no autopsy results are available and no other information is available regarding the cause of death, the Indeterminate category should be used.

We also include non-sudden deaths due to ventricular arrhythmia in the primary outcome definition. Deaths are categorized as such when a person suffers a cardiac arrest from an acute ventricular arrhythmia, is resuscitated and admitted to the intensive care unit, and then dies several days after the arrest from complications (e.g., neurological damage). Secondary outcomes for VEST are total mortality, non-sudden death and other cause-specific mortality (non-sudden fatal MI, other cardiac death, non-cardiac death, and indeterminate cause of death), hospitalization for MI, congestive heart failure, stroke/transient ischemic attack, ventricular arrhythmias, adverse events, LifeVest compliance, eventual ICD implantation, quality of life, and resource utilization/cost. The wearable defibrillator can do continuous ECG recording and monitor time worn. Therefore, data for several of the secondary outcomes that are analyzed within the intervention group will come from the LifeVest transmissions.

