+ - Includes information from medical records, death certificates, interviews of next-of-kin or personal physicians, and National Death Index searches

VF - Ventricular fibrillation; VT - Ventricular tachycardia; SVT - Supraventricular tachycardia; ICD - Implantable cardioverter defibrillator

stratified by length of follow-up period (to account for the higher expected rate in patients with 90 day follow-up), and randomization stratum, as jointly defined by EF and receipt of PCI and/or CABG during the hospitalization for the index MI.

We will also conduct a secondary "modified intention-to-treat" analysis of sudden death and death due to ventricular arrhythmia, total mortality, and other secondary outcomes. For this analysis, follow-up time will start at the time of discharge instead of randomization, and end 60/90 days after discharge, and participants who are randomized but die before discharge from the index hospitalization will be excluded. For death outcomes, this analysis will use the stratified exact methods specified for the primary analysis; for more common secondary outcomes, asymptotic methods will be considered.

We will also analyze treatment effects on overall mortality and non-sudden death, non-fatal cardiovascular events, ventricular arrhythmias, adverse events, LifeVest compliance, ICD implantation, quality of life and resource utilization/cost. For rare outcomes, exact methods will be used, as for the primary endpoint. For VEST therapies and hospitalizations, we will use the Anderson-Gill extension of the Cox model for repeated events, with robust standard errors, to better capture information from high-risk participants with repeated VEST therapies or hospitalizations.

We will also conduct a secondary, "as treated" analysis of sudden death and death due to ventricular arrhythmia, total mortality, and other secondary outcomes. The primary ITT analysis will estimate effectiveness of the vest, averaged over variations in compliance. We will attempt to estimate the efficacy of the vest for prevention of sudden death and death due to ventricular arrhythmia as well as total mortality using survival models treating observed vest use as a time-dependent covariate. For sudden death and death due to ventricular arrhythmia, we will

6

Protocol

use a Fine-Gray model treating other deaths as competing risks; a standard Cox model will be used for total mortality.

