1.5.12 Sample Size Calculations

When the trial was originally designed, the sample size for the VEST study was estimated to be 1,890. This assumed a power of 80%, with a 2-sided alpha of 0.05 and a 2:1 randomization scheme. The VEST sample size was carefully computed using data-based estimates of the following factors:

1. Mortality due to sudden death in the first 2 months following an MI in patients with $EF \le 35\%$ is 2.4%. The VALIANT Study, the EPHESUS Study, and the DINAMIT Study are three recent studies reporting on mortality and sudden death rates in the early period following an MI in populations similar to our study population. A meta-analysis of these three studies populations gives a summary estimate for sudden death rate of 2.4%.

2. Mortality due to sudden death in the first 3 months following an MI in patients with $EF \le 35\%$ is 3.0%. Using month-by-month data on sudden death in VALIANT, we estimate that extending follow-up from 2 to 3 months will increase the sudden death rate by 25%, from 2.4% to 3.0%. This accounts for declines in the sudden death rate in the weeks following MI.

3. Mortality due to ventricular arrhythmias in the first 3 months following an MI in patients with $EF \le 35\%$ is 2.73%. The wearable defibrillator vest will be effective at reducing only sudden death due to a ventricular arrhythmia. The preliminary data from the wearable defibrillation vest shows that 91% of all sudden cardiac arrests are due to ventricular arrhythmias. This is consistent with estimates in the literature. *Therefore*, 91% of 3.0% would give us an expected mortality of 2.73% due to ventricular arrhythmia.

4. The effectiveness of the wearable defibrillator to reduce sudden death due to ventricular arrhythmias will be 71.9%. Previous analyses show that the LifeVest conversion success rate is 98% for syncopal VT/VF. Based on early experience in VEST and planned changes in randomization procedures, we have targeted an intention-to-treat compliance rate with the LifeVest of 70%. This means that participants assigned to the LifeVest will wear it for 70% of all hours in the 3 months following randomization, including days when the LifeVest is not worn at all. However, since compliance and event rates are both anticipated to be highest in the earliest weeks of the trial we anticipate the LifeVest will be used during more than 70% of sudden death events. Thus, we estimate that the LifeVest will reduce sudden death due to syncopal VT/VF by 71.9%.

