AF	Atrial Fibrillation
AHA	American Heart Association
CABG	Coronary Artery Bypass Grafting surgery
CCC	Clinical Coordinating Center
CCU	Coronary Care Unit
CHF	Congestive Heart Failure
CMS	Centers for Medicare Services
CRF	Case Report/Record Form
CRT	Cardiac Resynchronization Therapy
DCC	Data Coordinating Center
DI	Detection Interval
DSMB	Data Safety Monitoring Board
ECG	Electrocardiogram
EF	Ejection Fraction
FVT	Fast VT
HRV	Heart Rate Variability
ICD	Implantable Cardioverter Defibrillator
IRB	Institutional Review Board
ITT	Intent-to-Treat
MI	Myocardial Infarction
MVP	Minimal Ventricular Pacing
NIH	National Institutes of Health
NHLBI	National Heart, Lung and Blood Institute
NID	Number of Intervals to Detect
NIPS	Non-invasive Programmed Stimulation
NSVT	Non Sustained Ventricular Tachycardia
QOL	Quality of Life
RNID	Number of Intervals to Redetect
PCI	Percutaneous Coronary Intervention
SVT	Supraventricular Tachycardia
VF	Ventricular Fibrillation
VT	Ventricular Tachycardia

VEST Statistical Analysis Plan

Version 1.0 to Version 1.1 (5/12/2012)

1. Primary endpoint revised from sudden cardiac death to sudden cardiac death or nonsudden death to ventricular arrhythmia (Section A, page 1).

Version 1.1 to Version 1.2 (12/5/2016)

- 1. Analysis of primary endpoint revised to use a simple chi-square test rather than exact stratified methods (Section A, page 1).
- 2. Section on Exploratory Analysis of Compliance added (Section B.4, page 2).

Version 1.2 to Version 1.3 (3/2/2017)

1. Plan is added for weighted sensitivity analysis of primary outcome omitting patients with indeterminate cause of death or unknown vital status (Section B.1.3)

VEST Statistical Analysis Plan

A. Primary Analysis

Treatment effects on the primary outcome, sudden death or non-sudden death due to ventricular arrhythmia, will be assessed using a chi-square test to compare incidence proportions in the VEST and control groups at 60/90 days after randomization. The test of the primary null hypothesis of no treatment effect will be conducted using a two-sided alpha of 5%. This analysis will be by intention to treat (ITT), according to treatment assignment, without regard to adherence to the assigned study intervention or other aspects of care.

B. Secondary Analyses

B.1. Sensitivity Analyses

Results will be checked for robustness in three planned sensitivity analyses.

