1. Modified intention to treat. We will omit from this analysis, patients who do not survive until discharge from the index hospitalization, and the 60/90 day follow-up will begin at the later event of randomization or discharge. The rationale is that the vest is essentially never worn in hospital, and so can provide no protection until after discharge. Although mortality is highest soon after a serious MI, close in-hospital monitoring is expected to keep the in- hospital death rate low. As part of this analysis, we will characterize times from randomization to discharge using histograms, stratified by group.

2. Adjustment for baseline imbalances. If we find substantial imbalances in powerful baseline prognostic variables with the potential to confound treatment assignment meaningfully, we will perform a sensitivity analysis using a logistic regression model to adjust for these factors. If more than two factors need to be adjusted for, we will summarize them using propensity scores [Rosenbaum 1983], then use a logistic model to adjust for the scores as a three-knot cubic spline, requiring two basis functions, so that the conservative rule of thumb of approximately 10 events per variable is observed [Vittinghoff 2006].

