3. Inverse weighting to deal with indeterminate cause of death and missing vital status. In the primary analysis, participants with indeterminate cause of death or missing vital status will be assumed not to have had a primary study event. In two secondary analyses, we will restrict the analysis to deceased participants with determinate cause of death and those known to be alive, weighting these observations so that their baseline correlates of the primary outcome are representative of the entire randomized cohort. To do this, we will develop two logistic models: the first for having determinate cause of death among all patients known to have died, and the second for having known vital status among all participants. Weights will be calculated as the inverse of the product of the fitted probabilities from these two models, after assigning a fitted probability of 1 from the first model for patients known to be alive. Variables in each model will be selected, without regard to the primary outcome, from a list of known correlates of the primary study outcome, as specified by Drs. [name], [name], and [name]. To deal with missing values of the candidate variables in the *a priori* list, multiple imputation will be used, followed by averaging of the weights obtained from each of ten completed datasets. Two versions of this sensitivity analysis will be conducted, the first excluding and the second using information from the vest in

determining vital status. The weighted analyses will use procedures properly accounting for the slightly smaller sample size available for analysis.

B.2. Heterogeneity of treatment effects

• By randomization stratum. We will use a logistic model to assess heterogeneity of the treatment effect across the 6 randomization strata jointly defined by EF, PCI, and CABG, as well as across the 2 strata defined by EF and the 3 strata defined by PCI and CABG. Nominal differences across strata will be conservatively interpreted in the light of tests for interaction between treatment and stratum, using a Bonferroni-corrected two-sided alpha of 0.05/3=0.0167. In additional exploratory analysis, we will assess modification of the ITT treatment effect by drugs, NYHA class, BMI, gender, and compliance

B.3. Treatment effects on secondary endpoints

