• *Total mortality, revascularization, ICD implantation*. Treatment effects on these binary secondary endpoints will be analyzed using chi-square tests, as proposed for the primary analysis. Logistic regression will be used to adjust for baseline imbalances as needed.

• *Re-infarctions and hospitalizations*. Treatment effects on these potentially recurring outcomes will be analyzed using the Anderson-Gill extension of the Cox model for recurrent events, with robust standard errors [Therneau 2000], to account for potential clustering of recurrent outcomes within participants.

 Vest-related symptoms. Fisher's exact tests will be used to compare frequency of potentially vest-related symptoms currently tabulated in the DSMB report, including fatigue, back pain, trouble sleeping, and upper body rash and itching.

B.4. Exploratory analysis of compliance

Factors associated with compliance with the VEST will be examined in an exploratory, hypothesis- generating analysis focusing on seasonality, site, geographic region, body mass index (BMI), time on study, baseline EF, as well as age, gender, race/ethnicity, education, marital and employment status, NYHA Class, and length of hospital stay. The analysis will use two-part models for repeated daily compliance measures, the first a GEE logistic model for any use of the VEST, and the second a GEE linear model for hours of use, transformed as necessary to meet normality assumptions, for patient-days where any use is detected. Inference for the combined effects of each proposed covariate on both elements of compliance (any use and hours of use among users) will be implemented using the seemingly unrelated estimation strategy. [Weesie, 1999]

C. References

- Weesie, J. 1999. sg121: Seemingly unrelated estimation and the cluster-adjusted sandwich estimator. Stata Technical Bulletin 52: 34–47. Reprinted in Stata Technical Bulletin Reprints, vol. 9, pp. 231–248. College Station, TX: Stata Press.

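### The protocol's as-treated efficacy analysis sets no time at which vest use is read; in its ordinary form it would favour the vest, and SAP v1.3 does not say whether the analysis is kept

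*Combined protocol and SAP*

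**What the plan says.** Protocol 1.5.11 separates the effectiveness of the vest (the intention-to-treat analysis) from its efficacy, which is to be estimated "using survival models treating observed vest use as a time-dependent covariate". For the primary outcome the authors will "use a Fine-Gray model treating other deaths as competing risks; a standard Cox model will be used for total mortality". The section does not give the time at which use is read, any lag, the scale of use (any use, hours, current status), or whether controls enter the model. Protocol 2.6 still names section 1.5.11 as the analysis plan.

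Three other places bear on how the model would behave:

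- Protocol 1.5.9 puts in the primary outcome a person who has a ventricular-arrhythmia arrest, "is resuscitated and admitted to the intensive care unit, and then dies several days after the arrest from complications".
- SAP B.1 item 1 says, of the index stay, that "the vest is essentially never worn in hospital, and so can provide no protection until after discharge".
- Protocol 1.5.12 item 4, in the power argument, says "we anticipate the LifeVest will be used during more than 70% of sudden death events".

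SAP v1.3 uses compliance in two ways. In B.2, as an exploratory modifier: "we will assess modification of the ITT treatment effect by drugs, NYHA class, BMI, gender, and compliance". In B.4, as an outcome: "Factors associated with compliance with the VEST will be examined in an exploratory" analysis. Neither is an as-treated model of death, and the SAP does not say whether the 1.5.11 analysis is dropped.

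**The concern.** There are two problems. First, the protocol commits to an analysis that the later SAP neither contains nor withdraws, so whether it is run could be settled after results are known.

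Second, if it is run as described, a time-dependent covariate takes its current value at the event time, and the event here is death. A person who arrests while wearing the vest, reaches intensive care and dies there days later has no vest on at death, so the death is assigned to non-use. The misassignment runs one way, because delayed deaths that began on the vest leave the use group and none enter it. The Cox model for total mortality is exposed in the same way to any in-hospital death after the vest has come off.

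A lesser point concerns Fine-Gray. It keeps people in the risk set after a competing death, when vest use is undefined, so the resulting ratio has no clear efficacy meaning.

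This is the only analysis the protocol describes as estimating efficacy. The revision summary for version 3.2 reports wear time below target, which makes an efficacy estimate more attractive to report.

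**Working it through.** The plan gives no figure for this analysis, so there is none to reproduce. Its event count can be built from stated values and checked against the design.

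**Inputs from the documents**
- Final sample size 2300 and composite rate 1.66% (1.5.12): E = 2300 × 0.0166 = 38.2 events. The design rates imply almost the same overall rate: (3.0% + 2 × 1.02%)/3 = 1.68%.
- Allocation 2:1 and target wear of 70% of hours (1.5.12). Because wear ran below target, 60% and 50% are shown too.

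**Assumption, not in the documents:** the share d of primary events that are delayed intensive-care deaths, taken as 5%, 10% and 20%.

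**Bias with no true effect, both arms pooled, use read at death**

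The share of person-time in use is w = wear × 2/3, which is 0.467, 0.400 and 0.333. Events counted under use are (1−d)wE. Events counted under non-use are [(1−d)(1−w) + d]E. Dividing each by its person-time, the ratio is

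(1−d)(1−w) / [(1−d)(1−w) + d].

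At 70% wear and d = 10%: 0.90 × 0.533 = 0.480, and 0.480/(0.480 + 0.10) = 0.83.

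| Wear | d = 5% | d = 10% | d = 20% |
|---|---|---|---|
| 70% | 0.91 | 0.83 | 0.68 |
| 60% | 0.92 | 0.84 | 0.71 |
| 50% | 0.93 | 0.86 | 0.73 |

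If controls are left out, w = 0.70 at 70% wear and the same formula gives 0.85, 0.73 and 0.55.

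A simulated Cox model with a daily covariate (400,000 people, 70% wear, death 4 days after a delayed arrest) gave 0.81 at d = 10%, 0.69 at d = 20%, and 1.01 with no delayed deaths. If the true ratio is 0.50, the closed form (1−d)×0.5/[1 + d×0.5×w/(1−w)] gives 0.43 and 0.37 at d = 10% and 20%.

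**Precision and false benefit**

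The standard error of the log ratio is 1/√(38.2 × 0.467 × 0.533) = 0.324. The 95% limits are the estimate multiplied and divided by exp(1.96 × 0.324) = 1.89.

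The simulation under no effect used 8,000 trials per setting, Poisson(38.2) events, hazard falling as exp(−t/45), wear falling 20 points over 90 days, death 2 to 7 days after a delayed arrest, and a Wald test. For d = 0, 5, 10 and 20%, false significant benefit was:
- 70% wear: 2.3%, 4.1%, 7.9%, 19.9%
- 60% wear: 2.2%, 3.4%, 6.7%, 15.4%

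A second simulation of 4,000 trials per setting at 70% wear gave 2.2%, 4.4%, 8.2% and 22%. With event and exposure both dated at the arrest, the ratio was 1.00 and false benefit 1.9 to 2.4%.

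**Fine-Gray**

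Assume competing deaths of 1.5% to 6%, so that on average s = 0.75% to 3% of the risk set has already died, and set use after death to 0. The ratio is multiplied by [(1−w)(1−s) + s]/[(1−w)(1−s)] = 1.014 to 1.058, towards less benefit. Carrying the last use forward gives a shift near zero.

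**The case against.** The strongest reply is that silence is being read as a rule. Section 1.5.11 states no timing and describes an attempt. The sample-size section points the other way: an effectiveness of 71.9% with 98% conversion implies use at 0.719/0.98 = 73.4% of events, so status at the event is plainly what the designers had in mind. The Operations Manual, which might hold coding rules, is not available. The statement that the vest is not worn in hospital concerns the index stay. All this stands. A reader might infer that the documents direct on-vest arrests to be coded as non-use; they do not. That is what the named method does when nothing further is specified.

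A reader might also infer from the SAP's change log, which records "Analysis of primary endpoint revised to use a simple chi-square test rather than exact stratified methods" but no removal of an as-treated model, that the omission was an oversight. The log compares SAP versions only, and nothing shows that an earlier SAP contained the model. The omission may be deliberate.

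The delayed-death share is assumed, and at 5% the distortion is small against limits of 1.9-fold either way. The simulated hazard is also slightly more front-loaded than the protocol's: it puts 85% of 90-day events in the first 60 days, against 2.4%/3.0% = 80% in 1.5.12. The closed-form ratios do not use a hazard shape.

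Finally, it is tempting to add that unworn inpatient days bias the result. That is not established. The effect vanishes if stays are identical and reverses (1.02 to 1.06) if the in-hospital hazard is half the home hazard. The SAP itself expects few in-hospital deaths. It forms no part of this point.

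**Conclusion.** The point holds in conditional form. It is certain that 1.5.11 plans the analysis, that 2.6 still points to it, and that SAP v1.3 neither includes nor withdraws it. If the analysis is run in its ordinary form, the direction of bias is firm: towards the vest. This rests on two inferences, that use is read at death and that the vest is off in a later intensive-care stay as in the index stay.

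The size is not known. It ranges from minor (ratio 0.91, false benefit about 4%) to material (0.68, about 20%) as the assumed delayed-death share goes from 5% to 20% at 70% wear. It is somewhat smaller at lower wear and larger if controls are excluded. For total mortality the size cannot be given, because the share of deaths in hospital is not stated. The Fine-Gray objection is one of meaning, with little numerical effect.

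A reader might carry this over to the trial's main result. The documents do not support that: the primary intention-to-treat comparison does not use wear data.

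**What to change.** State in the SAP whether the as-treated analysis is withdrawn or kept. If it is kept:

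1. Replace Fine-Gray with a cause-specific Cox model, censoring at other deaths.
2. Start the clock at the later of randomization or discharge, as in the SAP's modified intention-to-treat analysis.
3. Define one exposure scale, for example any use or hours worn on the last complete day, and apply the same one-day lag to cases and to everyone in the risk set.
4. For deaths after a resuscitated arrest, date the event at the arrest. Take the date from the records and narratives already collected under 1.5.9, not from vest recordings, which exist only for wearers.
5. For total mortality, date exposure for in-hospital deaths at the last complete day before the terminal admission.
6. State whether controls are included.

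The cost is SAP wording and modest programming, since wear time is already recorded for each day. Re-dating would touch about 2 to 8 of 38 primary events if 5% to 20% are delayed (0.05 × 38.2 = 1.9; 0.20 × 38.2 = 7.6), but the lag applies to all of them. Lagged daily wear is a coarser measure than status at the moment of arrest. Some onset dates will be incomplete, deaths before index discharge drop out, and intervals widen somewhat.

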
5. Given the above assumptions, we estimate an overall sudden death rate of 3.0% in the control group and 1.02% in the wearable defibrillator group (67% reduction in sudden death). The absolute reduction in mortality is the mortality from ventricular arrhythmia (2.73%) times the effectiveness of the LifeVest (71.9%) = 1.98%. Thus, the sudden death rate in the defibrillator LifeVest group is expected to be the mortality in the control group minus the absolute reduction or 3.00%-1.98% = 1.02%.

6. Given the short follow-up period (3 months) and strong efforts to collect complete data, we anticipate minimal loss to follow-up and minimal crossover. Crossover in the treatment group (LifeVest group) is accounted for in #4 above (some patients will not tolerate the LifeVest). Given that the LifeVest is only available by prescription, we expect that crossover from the control group to the treatment group will be exceedingly rare.

7. A power of 80%, with a 2-sided alpha of 0.05 and a 2:1 randomization scheme. Using these estimated event rates, a 2:1 randomization scheme and the standard formula for two-group comparisons of proportions, we will need a sample of 1260 in the wearable defibrillator group and 630 in the control group, or 1890 total participants.

Updating the Sample Size for VEST: We recognized that this sample size calculation is sensitive to the values of the inputs noted above. This raises the concern that the VEST trial might fail to reach firm conclusions despite the

Protocol

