anticipated efficacy. Rates of total mortality, sudden death and death due to ventricular arrhythmia, and LifeVest compliance are especially important drivers of sample size, and these are easily monitored during follow-up. We therefore plan to update our sample size after 1000 participants have completed their VEST follow-up and then again after 1500 participants have completed follow-up. We will use interim overall rates of total mortality and sudden death and death due to ventricular arrhythmia, as well as LifeVest compliance and crossover rates (off-protocol use of the LifeVest in the NO VEST arm), in conjunction with our original assumptions about the proportion of all sudden deaths that are due to ventricular arrhythmias and the efficacy of the LifeVest in preventing these potential events. We will also account for time in the hospital after randomization but before discharge (using real estimates of time-to-discharge from the study), during which the LifeVest is typically not worn and when we expect no differential effect on mortality to be induced by assignment to VEST. Because this procedure is blinded to treatment assignment, no meaningful inflation of the type-I error rate is expected.^{11,12}

The following limits will be adhered to when updating the sample size:

- The sample size will be updated only if the revised sample size is more than 10% larger than the planned value of 1900, i.e., greater than 2100.
- The updated sample size will not exceed 4,000 (twice the current planned sample size).
- No decrease in the planned sample size will be allowed (outside of the direction of the DSMB).

FINAL SAMPLE SIZE: In October 2015, after 1500 participants completed follow-up, the VEST Data and Safety Monitoring Board (DSMB) reviewed the blinded sample size re-estimation calculations and was concerned that with the estimated power at the current sample size (n=1890) there is a substantial likelihood of type II error. Therefore, the DSMB recommended that the VEST sample size be increased in order to achieve an estimated power of at least 70%, with a composite sudden death rate in the trial of 1.66%.

On April 25, 2016, the VEST Steering Committee approved the increase in sample size to a total of 2300 participants.

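### The only analysis labelled efficacy compares self-selected worn with unworn vest time with no stated adjustment, and its Fine-Gray version has no defined exposure after a competing death

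*Combined protocol and SAP*

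**What the plan says.** Protocol section 1.5.11 separates two questions. Intention to treat answers effectiveness, averaged over compliance. Efficacy, for both the primary outcome and total mortality, is to be attempted in a secondary as-treated analysis "using survival models treating observed vest use as a time-dependent covariate". For the primary outcome the protocol will "use a Fine-Gray model treating other deaths as competing risks; a standard Cox model will be used for total mortality". It names no covariates, weights or lag, and no value for vest use after a competing death.

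SAP v1.3 (March 2017) is later than protocol v3.2 (June 2016) and contains neither the as-treated analysis nor a Fine-Gray model. Compliance appears there only as an exploratory modifier of the intention-to-treat effect (B.2) and as an outcome in B.4: "Factors associated with compliance with the VEST will be examined in an exploratory" analysis. Protocol section 2.6 still directs analysis to section 1.5.11, so the as-treated analysis has not clearly been dropped.

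The candidate correlates of wear in B.4 include baseline EF, NYHA class, age and length of hospital stay. Protocol section 1.5.6 calls EF a strong predictor of mortality.

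**The concern.** Participants decide when to wear the vest, so comparing worn with unworn time gives up the protection of randomisation. Two mechanisms matter.

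- **Who wears it.** If frailer participants wear it less, worn time belongs to people at lower risk.
- **When it comes off.** If the vest is removed as someone deteriorates, the death falls in unworn time. SAP B.1 says the vest is hardly ever worn in hospital. That is written of the index stay; if it also holds on readmission, in-hospital deaths count as unworn.

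Both mechanisms affect the Fine-Gray and the Cox model alike. The Fine-Gray model has a further gap: its risk set retains participants who have died of other causes, for whom vest use does not exist.

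The revision summary for v3.2 reports wear below target, and the power goal at re-estimation was at least 70%. A null or diluted intention-to-treat result is therefore foreseeable, and the estimate labelled efficacy would then carry weight in interpretation.

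**Working it through.** **Plan's own figure.** The plan gives none for this analysis. Its sample size does reproduce. With "an overall sudden death rate of 3.0% in the control group and 1.02% in the wearable defibrillator group", two-sided 0.05, 80% power and 2:1, the continuity-corrected two-proportion formula gives 623 controls and 1,869 in all, against the stated 1,890 (1,869/1,890 = 0.989). The design rates are used below as they stand.

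**Inputs from section 1.5.12.** Vest share v = 2/3; target wear 70% of hours; risk 2.4% by 2 months and 3.0% by 3 months; final N 2,300; composite rate 1.66%. **Assumed, because the documents give no figures:** wear by risk group, hazard by wear group, vest removal before death, and the rate of other deaths.

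**Step 1: selection with a vest of no effect.** Class k has share p, relative hazard h and wear fraction w. All control time is unworn.

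- Worn time T1 = v·Σpw; worn events E1 = v·Σphw; all events E = Σph
- HR = (E1/T1) / [(E − E1)/(1 − T1)]

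Example: 40% at twice the hazard wear it 45% of the time, the rest 68%.

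- T1 = 2/3 × (0.18 + 0.408) = 0.392
- E1 = 2/3 × (0.36 + 0.408) = 0.512; E = 0.8 + 0.6 = 1.4
- HR = (0.512/0.392) / (0.888/0.608) = 1.306/1.461 = 0.894

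| Higher-risk group | Its wear | Wear in the rest | HR, true value 1 |
|---|---|---|---|
| 40% at 2× | 45% | 68% | 0.894 |
| 40% at 3× | 45% | 68% | 0.839 |
| 40% at 3× | 35% | 75% | 0.733 |
| 30% at 4× | 30% | 70% | 0.674 |

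A second set keeps mean wear at the 70% target: two thirds wear it 90% of days and one third 30% (2/3 × 0.9 + 1/3 × 0.3 = 0.70). If the hazard in good wearers relative to poor wearers is 0.67, the HR is 0.86; at 0.5 it is 0.76; at 1.5 it is 1.14.

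**Step 2: removal before death.** Replace E1 by (1 − q)·E1, where q is the share of deaths among wearers with the vest already off. With 70% wear and no other selection, T1 = 0.467.

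- q = 0.1: HR = (0.42/0.467)/(0.58/0.533) = 0.83
- q = 0.2: HR = (0.373/0.467)/(0.627/0.533) = 0.68
- q = 0.2 with the 0.5 hazard ratio of step 1: HR = 0.54

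**Step 3: false claims of benefit.** In 700 simulated trials of 2,300 with a null vest, nominal 2.5% in the direction of benefit, the as-treated model (cause-specific risk set) declared benefit in 20% (hazard ratio 0.5), 33% (q = 0.2) and 69% (both). Intention to treat stayed at about 2-4%. These runs used the design risk (3.0% × 2,300 = 69 events). With the 1.66% rate there are 0.0166 × 2,300 ≈ 38 events, and the false-positive rate falls. Using Φ(−1.96 − ln HR·√[D·0.467·0.533]), an HR of 0.74 gives 24% at D = 69 and 15% at D = 38.

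**Step 4: the Fine-Gray risk set alone.** No selection, null vest, 3% other deaths:

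- dead coded unworn: HR 1.02-1.03 (1.01-1.09 over 1-10% other deaths)
- last status carried forward: 0.99-1.00
- all vest-arm dead coded worn: 0.98-0.99

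**Step 5: vest coverage on the plan's own figures.** Section 1.5.12 sets 71.9% effectiveness and 98% conversion, so implied coverage at events is 71.9/98 = 73.4%, against 70% of hours. Dividing by hours gives 71.9/70 = 102.7% efficacy, which is impossible; dividing by event-weighted coverage returns 98%. The overstatement is 73.4/70 = 1.05, about 5%.

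**Step 6: room for adjustment.** About 38 events at the SAP's rule of roughly 10 per variable allow 3 to 4 terms.

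**The case against.** The analysis is secondary, the protocol says only that it will attempt it, and SAP v1.3 omits it. The absence of adjustment is inferred from silence. B.4 lists factors to explore and states no direction. Every bias size above rests on assumed wear and hazard patterns, and the bias can run the other way. All of this stands. It limits the weight of the point but does not answer it: section 2.6 keeps section 1.5.11 in force, and nothing in either document controls for the reasons the vest is worn or taken off.

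A reader might infer that the Fine-Gray risk set is what makes an ineffective vest look protective. Step 4 does not support that. Coding the dead as unworn moves the ratio slightly toward harm, and carrying the last status forward leaves it almost unchanged. Replacing Fine-Gray with a cause-specific model would therefore not remove the main bias.

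The randomisation-based alternative also has limits. Its exclusion assumption is more than the fact that an unworn vest cannot shock. Sections 1.5.4 and 1.5.5 give the vest arm weekly transmissions, calls to those with low wear, and release of rhythm strips with treatment changes recorded, all in an open-label trial. Its scale is also approximate if wear and individual risk are related. It does not, however, create benefit from a null intention-to-treat effect, provided that assumption holds.

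**Conclusion.** The point holds in limited form. The one analysis the protocol labels efficacy is confounded by self-selected wear in both of its models, with no adjustment stated. Under a vest with no effect, plausible but assumed selection gives hazard ratios of about 0.7 to 0.9, lower if selection and removal before death combine, and above 1 if sicker participants wear it more. The undefined exposure after a competing death is a separate and small specification gap, about 1-3% at an assumed 3% other deaths, with direction set by coding. A reader might also infer that the trial's main conclusion is at risk. It is not: the primary intention-to-treat test does not use wear. The change is worth making because it is cheap and because low wear makes the efficacy question likely to be asked.

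**What to change.** 1. Reconcile protocol section 1.5.11 with SAP v1.3: either state the efficacy analysis in the SAP or withdraw it.
2. Make the efficacy estimate randomisation-based: the intention-to-treat risk difference divided by the between-arm difference in vest coverage, with a bootstrap interval. Weight coverage by the expected timing of events, fixed in advance. The plan's own figures put 2.4/3.0 = 80% of the 3-month risk in the first 2 months.
3. State the exclusion assumption, and name vest-arm-only contact and rhythm unblinding as threats to it.
4. If a worn/unworn model is kept, use a cause-specific Cox model for the primary outcome with other deaths censored, so that exposure is defined for everyone at risk. Adjust for a small pre-specified baseline set, for example EF and a propensity-type score, within 3 to 4 terms; the full B.4 list is not feasible with about 38 events. Label the result observational, for total mortality as well, and say that baseline adjustment does not remove bias from vest removal shortly before death.

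The cost is wording in two documents and modest programming on data already held. The statistical price is a stated assumption and a wider interval: dividing by coverage of about 0.73 stretches the interval for the risk difference by roughly 1/0.73 ≈ 1.4.
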